10.3 Electrocardiogram

Descriptive statistics for ECG parameters (heart rate, RR interval, PR interval, QRS interval, QT interval, and QT corrected (QTc) interval at baseline and at the EOT Visit, and the change from baseline will be presented by treatment group. The QTc interval will be presented by both the Bazett (QTcB = $QT/(RR)^{\frac{1}{2}}$) and the Fridericia (QTcF = $QT/(RR)^{\frac{1}{3}}$)

corrections. The change from baseline to the minimum and maximum post-baseline values will also be summarized by treatment group. Baseline is defined as the value closest to but prior to the initiation of test article administration. If no value is available prior to the initiation of test article administration, a value within 2 hours after initiation of test article administration.

The number and percentage of subjects with any post-baseline increase in QTcF and any post-baseline increase of > 30 msec or > 60 msec in QTcF will be summarized by treatment group. The number and percentage of subjects with a baseline QTcF \leq 450 msec and with a post-baseline QTcF of > 450 msec and with a baseline QTcF \leq 500 and with a post-baseline QTcF of > 500 msec will also be summarized by treatment group. The number and percentage of subjects with a post-baseline increase in QTcF of > 30 msec resulting in a post-baseline QTcF of > 450 msec or > 500 msec will also be summarized by treatment group. Any post-baseline ECG includes unscheduled ECGs as well as the ECG completed at EOT. A listing will also be provided of subjects with a QTcF that meets one of the criteria listed above and will list all QTcF values for the subject.

The distribution of QTcF values ($\leq 450 \text{ msec}$, > $450 \text{ -} \leq 480 \text{ msec}$, > $480 \text{ -} \leq 500 \text{ msec}$, and > 500 msec) at EOT and the distribution of change from baseline in QTcF values at EOT (0 or less [no increase], 1-29 msec, 30-60 msec, and > 60 msec) will be summarized by treatment group.

10.4 Laboratory Values

Summaries of laboratory data will include hematology, chemistry, and coagulation (INR only) parameters. Laboratory parameters will be presented in alphabetic order with the following exceptions: differentials of white blood cell (WBC) counts will be presented following the WBC results, and chemistry parameters will first be grouped by organ class (renal, liver, electrolytes, and other) and presented alphabetically within each of these classes, as shown below.

Organ Class	Laboratory Parameter
Renal	Blood urea nitrogen (BUN)
Renal	Creatinine
Liver	Alkaline phosphatase (ALP)
Liver	Alanine aminotransferase (ALT)
Liver	Aspartate aminotransferase (AST)
Liver	Total bilirubin
Liver	Gamma-glutamyl transpeptidase (GGT)
Electrolytes	Calcium (Ca)
Electrolytes	Carbon dioxide (CO ₂)
Electrolytes	Chloride (Cl)
Electrolytes	Magnesium (Mg)
Electrolytes	Phosphorus (P)
Electrolytes	Potassium (K)
Electrolytes	Sodium (Na)

Table 10.Laboratory Parameters and Organ Class

Organ Class	Laboratory Parameter
Other	Creatinine phosphokinase (CK)
Other	Lipase

Table 10.Laboratory Parameters and Organ Class

Baseline is defined as the central lab value closest to and prior to the first dose of study drug. If no central lab value is available prior to the first dose of study drug, the local lab value that is closest to and prior to the first dose of study drug will be used as baseline. For by visit analyses, central lab values will be used unless no central lab value was obtained in the visit window. In this case, local lab values will be used for the by visit analyses. All lab values (central and local) are used for determination of the overall worst post-baseline value.

Several analyses of the laboratory data will be presented. Descriptive statistics (based on International System units) for chemistry, hematology and coagulation values, and the change from baseline will be summarized by treatment group at each time point (ECR Visit, EOT Visit and PTE Visit), and for the overall worst value post-baseline (which includes unscheduled visits). Appendix 4 provides the directionality of the worst values for each laboratory parameter.

Clinically notable laboratory values will be determined based on the modified Division of Microbiology and Infectious Diseases (DMID) criteria in Appendix 5. Shift tables will be presented to show the number of subjects with a laboratory value with a grade of 0, 1, 2, 3 or 4 at baseline versus the value at each visit and the worst post-baseline value. Number and percentage of subjects with at least a 2-grade increase from baseline (based on DMID criteria) will be summarized by treatment arm. Percentages for each laboratory test will be based on the number of subjects with a baseline and post-baseline evaluation of the specific laboratory test. A listing will be provided which gives all laboratory results for a given laboratory test for subjects who have at least one 2-grade increase from baseline.

The number and percentage (based on the number of subjects with a normal level at baseline) of subjects in each treatment group with an elevated transaminase level (> 3 × upper limit of normal [ULN], > 5×ULN, and > 10 × ULN), an elevated bilirubin level (> 1.5 × ULN and > 2 × ULN) will be presented by study visit. A listing of subjects who meet the laboratory criteria for Hy's law at the same visit will also be provided. The laboratory criteria for Hy's law is defined as 1) ALT or AST> 3 × ULN, ALP \leq 2.0 × ULN, and total bilirubin > 1.5 ULN and 2) ALT or AST> 3 × ULN, ALP \leq 2.0 × ULN, and total bilirubin > 2 × ULN.

Detailed subject listings of all laboratory data collected during the study (local and central laboratory data) will be provided, including calculated creatinine clearance (using the Cockcroft-Gault equation). Laboratory values outside normal limits will be identified in the subject data listings with flags for low (L) and high (H) as will laboratory values that meet the clinically notable thresholds (CN).

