Stop date for con meds	Non- Antibacterial	If it cannot be determined whether or not the stop date of a medication (nonantibacterial) is after the first dose of study drug, it will be assumed that the medication was received after the first dose of study drug
	Antibacterial	Missing stop dates for antibacterials will be queried for a value. If it cannot be determined whether or not the stop date of an antibacterial is after the first dose of study drug, it will be assumed that the medication was received after the first dose of study drug unless the indication notes that the medication was received prior to the first dose of study drug. If it cannot be determined whether the antibacterial was received prior to the assessment of Early Clinical Response, the EOT and/or the PTE Visit, the antibacterial will be assumed to have been received through the PTE Visit.

Laboratory Test	Parameter	Worst Value
Hematology	Hematocrit	Lowest value
	Red blood cell count	Lowest value
	Mean corpuscular hemoglobin	Lowest value
	Mean corpuscular hemoglobin concentration	Lowest value
	Hemoglobin	Lowest value
	Mean corpuscular volume	Lowest value
	White blood cell count	Lowest value
	Platelets	Lowest value
	Eosinophils/Differential	Highest Value
	Neutrophils	Lowest Value
Chemistry		
	Alkaline phosphatase (ALP)	Highest value
	Alanine aminotransferase (ALT)	Highest value
	Aspartate aminotransferase (AST)	Highest value
	Bicarbonate	Lowest value
	Blood glucose	Both highest value and lowest value
	Blood urea nitrogen	Highest value
	Calcium	Both highest value and lowest value
	Chloride	Both highest value and lowest value
	Creatinine	Highest value
	Creatine phosphokinase (CK)	Highest value
	Gamma-glutamyl transpeptidase (GGT)	Highest value
	Lipase	Highest value
	Magnesium	Both highest value and lowest value
	Phosphorus	Both highest value and lowest value
	Potassium	Both highest value and lowest value
	Sodium	Both highest value and lowest value
	Total bilirubin	Highest value
Coagulation	Prothrombin time international normalized ratio (INR)	Highest value

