Appendix 4 Directionality of Worst Laboratory Parameters

Appendix 5 Modified Division of Microbiology and Infectious Diseases Adult Toxicity Table

The DMID Adult Toxicity Table (21-NOV-2007) was modified to exclude the clinical component of the toxicity grading because clinical signs and symptoms related to abnormal laboratory values are not collected in this study. In addition, Grade 0 was added to the table so that shifts from normal could be analyzed. Grades for enzymes were modified as indicated in the table below.

For toxicity grades based on a multiple of the ULN, the normal range from the central laboratory will be applied.

For toxicity grades based on fixed values, the grades will be assigned regardless of the normal actual range values from the central laboratory. For example, a hemoglobin value of 10.0 gm/dL will be assigned a grade of 1 toxicity, even if the lower limit of normal from the laboratory was 9.8 gm/dL.

	HEMATOLOGY										
	Grade 0	Grade 1	Grade 2	Grade 3	Grade 4						
Hemoglobin (gm/dL)	> 10.5	9.5-10.5	8.0-9.4	6.5-7.9	< 6.5						
Absolute Neutrophil Count (count/mm ³)	> 1500	1000-1500	750-999	500-749	< 500						
Platelets (count/mm ³)	\geq 100,000	75,000-99,999	50,000-74,999	20,000-49,999	< 20,000						
WBCs (count/mm ³)	1000-10,999	11,000-12,999	13,000-14,999	15,000-30,000	> 30,000 or < 1,000						

	CHEMISTRY								
	Grade 0	Grade 1	Grade 2	Grade 3	Grade 4				
Hyponatremia (mEq/L)	> 135	130-135	123-129	116-122	< 116				
Hypernatremia (mEq/L)	< 146	146-150	151-157	158-165	> 165				
Hypokalemia (mEq/L)	> 3.4	3.0-3.4	2.5-2.9	2.0-2.4	< 2.0				
Hyperkalemia (mEq/L)	< 5.6	5.6-6.0	6.1-6.5	6.6-7.0	> 7.0				
Hypoglycemia (mg/dL)	≥ 65	55-64	40-54	30-39	< 30				
Hyperglycemia (mg/dL) (nonfasting and regardless of prior history of diabetes)*	< 116	116-160	161-250	251-500	> 500				
Hypocalcemia (mg/dL) (corrected for albumin)	> 8.4	8.4-7.8	7.7-7.0	6.9-6.1	< 6.1				
Hypercalcemia (mg/dL) (correct for albumin)	≤ 10.5	10.6-11.5	11.6-12.5	12.6-13.5	> 13.5				
Hypomagnesemia (mEq/L)	> 1.4	1.4-1.2	1.1-0.9	0.8-0.6	< 0.6				
Hypophosphatemia (mg/dL)	≥ 2.5	2.0-2.4	1.5-1.9	1.0-1.4	< 1.0				
Hyperbilirubinemia (total bilirubin)	< 1.1×ULN	1.1-1.5×ULN	> 1.5- 2.5×ULN	>2.5-5×ULN	> 5×ULN				
Urea	< 1.25×ULN	1.25-2.5×ULN	> 2.5-5×ULN	> 5-10×ULN	>10×ULN				
Hyperuricemia (uric acid) (mg/dL)	< 7.5	7.5–10.0	10.1–12.0	12.1–15.0	> 15.0				
Creatinine	< 1.1×ULN	1.1-1.5×ULN	> 1.5- 3.0×ULN	> 3.0-6×ULN	>6×ULN				

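### SAP Appendix 4 takes the lowest white cell count as the worst value, but Appendix 5 puts Grades 1 to 3 only on high counts, so SAP 10.4 should say what worst means in the graded shift table

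*SAP*

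**What the plan says.** **Direction of worst.** SAP 10.4 plans descriptive statistics by visit and for the overall worst post-baseline value. It adds that "Appendix 4 provides the directionality of the worst values for each laboratory parameter". In Appendix 4 the row "White blood cell count" is set to the lowest value. The values that feed it are broad: "All lab values (central and local) are used for determination of the overall worst post-baseline value". SAP 7.6 also brings in unscheduled visits.

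**Grading.** Appendix 5 grades WBC (count/mm³) as follows: Grade 0, 1,000 to 10,999; Grade 1, 11,000 to 12,999; Grade 2, 13,000 to 14,999; Grade 3, 15,000 to 30,000; Grade 4, "> 30,000 or < 1,000". It explains that "Grade 0 was added to the table so that shifts from normal could be analyzed".

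**Where the two meet.** The next paragraph of SAP 10.4 introduces the Appendix 5 grades and plans shift tables of grade "at baseline versus the value at each visit and the worst post-baseline value". It does not mention Appendix 4 again. It also plans a count of patients whose grade rises by two or more.

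**TEAE start.** In three places SAP 10.1 ties treatment emergence to the first *active* test article. Protocol 12.9.1 uses the first dose of test article, and SAP 6.1.2 counts placebo as test article.

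**The concern.** Appendix 4 is the only place where the SAP defines worst. A programmer who applies it to the graded shift table will grade the lowest WBC on a scale whose Grades 1 to 3 lie entirely on the high side. A count that rises and then normalises would be tabulated as no change or as improvement.

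High counts are expected here. WBC above 12,000 is one of the qualifying findings in Inclusion Criterion 5, so some patients should start at Grade 1 or higher. A graded shift table has to separate recovery from further worsening in these patients, and the lowest value cannot do that.

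At stake is the accuracy of one safety shift table and the completeness of one descriptive summary.

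**Working it through.** The plan states no figure to reproduce. The check applies the Appendix 5 grades to example series.

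**1. What the lowest-value rule can show.** Let m be the lowest post-baseline count. The table shows Grades 1 to 3 only if m is between 11,000 and 30,000, so every post-baseline count must be at least 11,000. It shows Grade 4 only if m < 1,000, or if m > 30,000, meaning that all counts are above 30,000. One count from 1,000 to 10,999, with none below 1,000, gives Grade 0 whatever the peak. Counts of 1,000 to 3,999 are Grade 0 as well, so on the low side the rule finds only counts below 1,000.

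**2. Example series.**

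| Baseline (grade) | Post-baseline counts | Grades | Shift by lowest value | Shift by highest grade | Rise of 2 or more grades |
|---|---|---|---|---|---|
| 9,000 (0) | 28,000; 8,500 | 3, 0 | 0 to 0 | 0 to 3 | yes |
| 13,500 (2) | 28,000; 10,200; 8,500 | 3, 0, 0 | 2 to 0 | 2 to 3 | no, 3 − 2 = 1 |
| 18,000 (3) | 34,000; 9,000 | 4, 0 | 3 to 0 | 3 to 4 | no, 4 − 3 = 1 |
| 9,000 (0) | 3,000; 800; 5,000 | 0, 4, 0 | 0 to 4 | 0 to 4 | yes |

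A sustained high series (16,000; 17,000; 15,500) is Grade 3 by either rule. In the last row the highest count, 5,000, would give Grade 0. Switching WBC to highest only would therefore lose counts below 1,000.

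**3. Is WBC the exception?** Eighteen parameters are in both appendices: haemoglobin, neutrophils, platelets, WBC, sodium, potassium, glucose, calcium, magnesium, phosphorus, bilirubin, urea, creatinine, AST, ALT, GGT, alkaline phosphatase and lipase. For 17 of them the Appendix 4 direction includes every graded side. WBC is the only one where it leaves out the side carrying Grades 1 to 3.

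**4. What other tables still show.** By-visit shift tables cover ECR, EOT and PTE. They use one value per window, central unless none was obtained. The 2-grade summary does not say which value it uses; I take it as any post-baseline value, in line with its companion listing. The largest possible rise from baseline Grades 0, 1, 2, 3 and 4 is 4, 3, 2, 1 and 0. The summary therefore never counts a rise from Grade 3, nor a one-grade rise from Grades 0 to 2.

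**5. The remaining gap.** Suppose baseline is 18,000, an unscheduled test gives 34,000, and the ECR and EOT values are 12,000 and 9,000. The by-visit tables show 3 to 1 and 3 to 0. The 2-grade summary does not count the patient. The worst-value table by lowest value shows 3 to 0. Grade 4 then appears in no laboratory summary table.

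**6. TEAE clock.** In Protocol Table 1, infusion 1 is active only in the omadacycline arm and infusion 2 only in the moxifloxacin arm. Leaving aside any gap between infusions:
- In numbered order, moxifloxacin starts its clock 30 minutes later (25 to 35) with BID dosing on Day 1, or 60 minutes later (55 to 65) with QD dosing.
- If the infusions run together, the difference is 0.
- In reverse order, omadacycline starts 60 minutes later (55 to 65).

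One hour is 1/720 = 0.14% of 30 days.

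**The case against.** The strongest objection is that Appendix 4 is cited only for the descriptive summary. The graded table is in a separate paragraph that opens with Appendix 5, and in a table of grades worst naturally means worst grade. This stands. A reader might infer that the SAP prescribes a wrong shift table, but it does not say so; the text is ambiguous. The ambiguity still needs settling: if worst means worst grade there, SAP 10.4 uses the word for WBC in two opposite senses without saying so.

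A reader might also infer that high counts vanish from the report. They do not. If the peaks in the table above fall at ECR, the by-visit shift table shows 2 to 3 and 3 to 4. Protocol 8.21.4 has clinically significant abnormalities outside the expected range recorded as AEs, Protocol 8.21.5 records worsening CABP as clinical failure, and SAP 9.4 summarises WBC at 72 to 120 hours. Listings hold every value.

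The lowest WBC is a sensible descriptive quantity for leucopenia, and that also stands. It is a reason to keep the low side, but not a reason to leave out the high side.

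**Conclusion.** The mismatch between Appendices 4 and 5 for WBC is real, and the meaning of worst in the graded shift table is not settled. If Appendix 4 governs that table, transient rises are tabulated as Grade 0. On either reading, the worst-value descriptive summary reports only low WBC.

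The loss is limited to the worst-value tables. What can drop out of the laboratory summary tables altogether is a peak that is not the by-visit value (an unscheduled or local test) with a rise of less than two grades, and then only if the graded table follows Appendix 4.

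It is tempting to attach a patient count. The documents give no post-baseline WBC distribution and no frequency of unscheduled tests, so any count would rest on assumed percentages. Nor is there a basis for inferring bias between arms: the rule is the same in both. The primary analysis is not affected.

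The TEAE wording is a genuine protocol-SAP mismatch but close to negligible: about an hour at most, plus any gap between infusions. A reader might infer that it favours one arm, but the infusion order is not stated, so the direction is unknown. AEs on that date with no recorded time count as treatment emergent in any case, and all AEs are listed.

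**What to change.** 1. In SAP 10.4, state that for graded shift tables the worst post-baseline value is the highest DMID grade over all post-baseline values (central, local and unscheduled). Where Appendix 5 has separate low and high rows, as for sodium, apply this to each row. For the other 17 shared parameters this agrees with Appendix 4.
2. In Appendix 4, set WBC to both highest and lowest value for the descriptive summary, as is already done for sodium, potassium and calcium. This alone would not repair the graded table, because a lowest-value graded row would still show worsening as improvement.
3. As a minor consistency edit, delete *active* in the three places in the TEAE definition of SAP 10.1, so that it matches Protocol 12.9.1 and the SAP's other clocks.

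The cost is one sentence, one cell, one extra WBC row and three deleted words. The Appendix 5 grades stay as they are, and no new data are needed.

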10.5 Physical Examinations

Subject listings of all physical examination results by body system will be provided. Physical examination results will be coded using MedDRA (Version to be delineated in the CSR). Any changes from baseline will be recorded as AEs.

11 RESOURCE UTILIZATION ANALYSES

Descriptive statistics of the following resource utilization parameters will be provided by treatment group:

- Number of days in the hospital from the time of initiation of test article until discharge. Subjects who are not admitted to the hospital will be assigned a value of 0 for number of days in the hospital. Analyses will also be completed by country due to varying clinical practices per country.
- Number of days in the hospital from the time of initiation of rescue antibiotic (ie, a second antibiotic) therapy until discharge. Analyses will be completed only for those subjects admitted to the hospital and who required a second antibiotic therapy (ie, were treatment failures) and separately for all subjects. For the latter, subjects who are not admitted to the hospital or who did not require a second antibiotic therapy will be assigned a value of 0 for number of days in the hospital. Analyses will also be completed by country.
- Number of days in the hospital from the time of admission for CABP until discharge. Subjects who are not admitted to the hospital will be assigned a value of 0 for number of days in the hospital. Analyses will also be completed by country.
- Number of hospital re-admissions after discharge from the hospital for the CABP admission through the Final Follow-up Visit will be summarized.
- Number of emergency room/department and physician visits after discharge from the hospital for the CABP admission through the Final Follow-up Visit will be summarized.

12 OTHER RELEVANT DATA ANALYSES/SUMMARIES

12.1 Protocol Deviations

A listing of all protocol deviations will be provided. Deviations will also be reviewed by the Sponsor and categorized into general categories such as: randomization, at least one inclusion criterion not met, at least one exclusion criteria met, study procedures/visits not done, study visit outside window, noncompliance with dose, and use of prohibited medications or treatments, consent-Institutional Review Board compliance issues, etc. The Sponsor will also categorize the protocol deviations as major and minor. Review of protocol deviations will be conducted and finalized prior to unblinding the database. The number of subjects with at least one protocol deviation, the number of subjects with a major protocol deviation, and the number of subjects with at least one major deviation in each category will be presented by treatment group for the ITT population. A major deviation is defined as one that potentially affects the efficacy and/or safety analyses.

12.2 Prior and Concomitant Medications

All medications taken within 7 days prior to the date of informed consent through the Final Follow-up Visit will be recorded on the eCRF. Prior medications will be summarized by WHODRUG (Version to be delineated in the CSR) Anatomical Therapeutic Chemical Classification (ATC) level 3 (third level indicates the therapeutic/pharmacologic subgroup) and generic medication name. Medications are considered prior if taken prior to the first infusion of test article or if their start date is unknown. Subjects will be counted only once for an ATC class and generic medication name. Concomitant medications taken during and after the study treatment period will be similarly summarized. Medications are considered concomitant if taken on or after the first infusion of test article, or if their stop date is unknown or marked as continuing.

The number and percentage of subjects who receive the following prior and concomitant medications will be summarized by treatment group:

- Systemic antibacterial medications taken within 72 hours prior to first infusion of test article and the reasons for receipt (ITT and CE-PTE populations)
- Systemic antibacterial medications (excluding test article) taken between first infusion of test article and the EOT Visit (CE-EOT population) and the reasons for receipt
- Systemic antibacterial medications (excluding test article) taken between first infusion of test article and the PTE Visit (CE-PTE population) and the reasons for receipt
- Non-antibacterial medications taken prior to informed consent through the first infusion of test article (ITT and Safety populations)
- Non-antibacterial medications taken from the first infusion of test article through the Final Follow-up Visit (ITT and Safety populations)

Appendix 1Schedule of Assessments and Procedures

Study Phase	Screening ^b		iv tment				iv o	r po T	reatm	ent					EOT a	and Follo	ow-up
Study Day ^a	-1	1	2	3	4 inpatient only	5	6 inpatient only	7 ^d	-	9 atient nly	10	11 inp	12 Datient of	13 only	EOTe	PTE	FFU ^f
					← 1	ECR visit nust occur 7 to 120 hours fter first dos c	\rightarrow			ntinuin isit. Tr	g and t eatmer subjec	his is n 1t past 1	reatmer ot the H 10 days bactere	EOT is		5 to 10 days after last day of therapy	30 to 37 days after Day 1
Screening and eligibility procedures																	
Signed informed consent ^g	X																
Medical history, current medical conditions, demography	X																
Assessment of CABP symptom severity ^h	X		Х	Х	Х	Х	Х	Х	Х	Х	Х	Х	X	X	X	X	
Chest X-ray or CT scan ⁱ	Х																
PORT risk class, ABG (or pulse oximetry) ^j	X																
Blood and urine samples for local lab hematology/chemistry/pregnancy ^k	X																
SF-36v2 [®] Health Survey	Х																Х
Review of Inclusion/Exclusion criteria	Х																
Randomization (if Eligible)		Х															
Clinical Procedures and Test Article A	Administration	1															-
Test article administration and accountability ¹		X	Х	Х	Х	Х	Х	Х	Х	Х	Х	Х	X	X			
Physical examination ^m	Х		Х	Х	Х	Х	Х	Х			Х				Х		
Vital signs ⁿ	Х	Xo	Xo	Х	Х	Х	Х	Х	Х	Х	Х	Х	Х	Х	Х		
12-lead ECG ^w	Х														Х		
Blood for central lab tests: hematology/chemistry/pregnancy	Xp					Х									Xp	Xp	
AEs, SAEs, and mortality ^q	Х	Х															Х
Prior & concomitant medications ^r	X	Х															Х
Plasma samples (in heparin) for PK analyses ^s		X				X											

Study Phase	Screening ^b		iv iv or po Treatment						EOT a	EOT and Follow-up							
Study Day ^a	-1	1	2	3	4 inpatient only	5	6 inpatient only	7 ^d	8 npatie	9 ent only	10	11 inp	12 atient o	13 nly	EOT ^e	PTE	FFU ^f
Assessment for po switch or need for continued therapy ^t				Х	C									X			
Investigator's Assessment of Clinical Response															Х	Х	Х
Assessment of Resource Utilization		X															X
Microbiological Procedures	•																
Blood culture ^u	X					As C	linically	/ Indi	cated								
Respiratory culture & Gram stain ^v	Х														Х	Х	
Urine for Local lab Legionella pneumophila and Streptococcus pneumoniae antigen test	X																
Blood for Central lab Legionella pneumophila, Mycoplasma pneumoniae & Chlamydophila pneumoniae serology	X															Х	

ABG = arterial blood gas, AE = adverse event, BP = blood pressure, β -hCG = beta-human Chorionic Gonadotropin, CABP = community-acquired bacterial pneumonia, CT = computed tomography, CXR = chest X-ray, ECG = electrocardiogram, ECR = Early Clinical Response, eCRF = electronic case report form, EOT = end of treatment, FFU = final follow-up, ICF = informed consent form, iv = intravenous, IxRS = interactive voice/web response system,

PK = pharmacokinetics, po = per oral, PORT = Pneumonia Patient Outcomes Research Team, PTE = post-therapy evaluation, RR = respiratory rate, SAE = serious adverse event.

^a Study Day 1 is the first day of test article administration. Subsequent study days may be consecutive calendar days.

^b Following the signing of an ICF, all Screening evaluations (except radiographic confirmation of pneumonia), should be completed within the 24 hours prior to randomization. The radiographic confirmation of pneumonia should be completed within the 48 hours prior to the first dose of test article.

^c The ECR visit must be conducted within 72 to 120 hours after the first dose of test article; the study day for this visit could be on Days 4, 5, or 6, depending on the time of the first dose of test article. Subjects who remain hospitalized (inpatients) during study treatment will have daily assessments. For subjects who are not hospitalized, only 1 visit is required between Study Days 4 to 6.

^d If the investigator determines that no additional treatment is required beyond Day 7, the Day 7 visit can be considered the EOT visit and a separate EOT visit is not required.

^e To be conducted on the day of, or within 2 days following the last dose of test article. Should also be conducted for any prematurely withdrawn subject on the day of, or within 2 days following the last dose of test article.

^f The Final Follow-up assessment may be conducted via telephone contact or by another interactive technology for subjects who were considered to be Clinical Successes and had no ongoing AEs, clinically significant laboratory findings or ECG abnormalities noted at or after the PTE visit. Otherwise, the visit must be conducted in person.

^g Written and signed ICF must be obtained before any study assessment is performed.

^h The investigator should assess the severity of the subject's CABP symptoms of cough, sputum production, pleuritic chest pain, and dyspnea based upon the Community-Acquired Bacterial Pneumonia Subject Symptom Severity Guidance Framework for Investigator Assessment (Appendix 3 of the protocol).

ⁱSubjects must have a confirming CXR or CT scan consistent with acute bacterial pneumonia within the 48 hours prior to the first dose of test article. ^jOnly subjects with a PORT Risk Class of III or IV are eligible for enrollment.

^k Local laboratory hematology and chemistry evaluations required for assessing subject eligibility, including (at minimum): white blood cell count, serum transaminases and bilirubin levels, and serum or urine pregnancy test (for women only).

¹Subjects should receive their first dose of test article within 4 hours after randomization. The total duration of test article therapy (iv plus po) for all subjects will be 7-10 days (up to 14 days for subjects with bacteremia identified at Screening). The pharmacist or designee will be unblinded to prepare appropriate iv doses of the IxRS identified test article. An unblinded field monitor will perform drug accountability and review the pharmacist's records. Oral test article may be dispensed and reconciled by blinded or unblinded personnel. All oral doses should be taken in a fasted state (no food, antacids or multivitamins containing multivalent cations [eg, aluminum, magnesium, calcium, bismuth, iron, or zinc] or drink except water for at least 4 hours before dosing). After dosing, no food is permitted for 2 hours as well as no dairy products, antacids, or multivitamins containing multivalent cations (eg, aluminum, magnesium, calcium, bismuth, iron, or zinc) for 4 hours. Subjects discharged with po test article will be asked to return all unused test article and packaging at each visit.At the EOT visit subjects discharged with po test article will return any remaining unused po test article and site staff will perform accountability.

^m A full physical examination will be completed at Screening. Thereafter, abbreviated physical examinations may be performed at the indicated timepoints. Additional physical examinations may be performed as clinically indicated.

ⁿVital signs include body temperature, BP, pulse oximetry, heart rate, and RR.

^o Blood pressure and heart rate should be measured within 30 minutes before, and approximately 1 hour (± 15 minutes) after the completion of the infusions on Day 1 and Day 2.

^pBlood will be collected from all female subjects for a serum β-hCG pregnancy test at the Central Laboratory at the Screening, EOT and PTE visits.

^qAEs and SAEs will be recorded from the time of signing of the ICF to the Final Follow-up assessment.

^r Medications administered within the 7 days prior to the date of signing the ICF or during the Screening phase will be recorded in the eCRF, as will all medications and significant non-drug therapies administered after the first dose of test article.

^s PK sample collection to occur on Day 1 (2 to 3 hours after the start of Dose 1) and at the ECR visit (Days 4 to 6; at any time during the visit).

^t At any time after the second day of iv treatment (Day 2), the subject may be switched to po medication based upon determination of clinical stability. Refer to Section 7.6.5 of the protocol for required criteria to switch to po treatment. The first po dose should be administered in the morning, 12-24 hours after the last iv dose. Test article administration and total duration of study treatment are outlined in footnote l.

^u If bacteria are isolated from baseline blood cultures, repeat blood cultures must be collected on the day that the positive blood culture is detected. If subsequent blood cultures are also positive, repeat the blood cultures as necessary until negative blood cultures are obtained.

^v Culture and Gram stain from an adequate quality sputum specimen or other respiratory specimen. At the EOT and/or PTE visit, respiratory specimen cultures and Gram stains should be obtained only for subjects who are Clinical Failures and require alternative antibacterial treatment for CABP.

^w Additional ECGs can be performed as clinically indicated, at the discretion of the investigator.

	72 to 120 hours post first dose	End of Therapy Visit (EOT)	Post Treatment Evaluation Visit (PTE)
ITT	ECR	IA	IA
MicroITT	ECR	Micro (by subject)	IA
	ECR (by pathogen)	Micro (by pathogen)	IA (by pathogen)
	ECR (by pathogen and		IA (by pathogen and MIC)
	MIC)		Micro (by subject)
			Micro (by pathogen)
CE-EOT		IA	
CE-PTE			IA
ME-EOT		Micro (by subject)	
		Micro (by pathogen)	
ME-PTE			IA
			IA (by pathogen)
			IA (by pathogen and MIC)
			Micro (by subject)
			Micro (by pathogen)

